7.1.6. Summaries of Adverse Events and Deaths

Treatment-emergent AEs will be summarized based on the Safety Analysis Set.

7.1.6.1. Summaries of AE Incidence

The number and percentage of subjects who experienced at least 1 TEAE will be provided and summarized by SOC, HLT, PT, and treatment group. For other AEs described below, summaries will be provided by SOC, PT, and the treatment group:

- TEAE (by maximum severity)
- TEAEs with Grade 3 or higher (by maximum severity)

- TE treatment-related AEs (by maximum severity)
- TE treatment-related AEs with Grade 3 or higher (by maximum severity)
- TE SAEs
- TE treatment-related SAEs
- TEAEs leading to premature discontinuation of any study drug
- TEAEs leading to premature discontinuation of study
- TE AEs leading to death (i.e., outcome of death)
- TEAEs leading to temporary interruption of any study drug

A brief, high-level summary of the number and percentage of subjects who experienced at least 1 TEAE in the categories described above will be provided by treatment group. All deaths observed in the Main Study will also be included in this summary.

Multiple events will be counted only once per subject in each summary. Adverse events will be summarized and listed first in alphabetic order of SOC (and HLT within each SOC if applicable), and then by PT in descending order of total frequency within each SOC. For summaries by severity grade, the most severe grade will be used for those AEs that occurred more than once in an individual subject during the study.

In addition to the above summary tables, all TEAEs will be summarized by PT only, in descending order of total frequency.

In addition, data listings will be provided for the following:

- All AEs, indicating whether the event is treatment emergent
- All SAEs
- All Deaths
- All SAEs leading to death (i.e., outcome of death)
- All AEs with severity of Grade 3 or higher
- All AEs leading to premature discontinuation of any study drug
- All AEs leading to premature discontinuation of study
- All AEs leading to temporary interruption of any study drug

7.1.7. Adverse Events of Special Interest

Events of interest will be identified by the use of either SMQs or MedDRA search terms (MSTs). However, should additional cases not detected by the predefined search term listings identified during the clinical review process, these cases will also be reported by respective category.

7.1.7.1. Adjudication Committee for Major Adverse Cardiovascular Events (MACE) and Thromboembolic Events

An independent adjudication committee governed by a charter will be set up to perform adjudication of potential MACE as well as thromboembolic events reported during the study.

7.1.7.1.1. Major Adverse Cardiovascular Events (MACE)

MACE will be comprised of cardiovascular (CV) death, non-fatal myocardial infarction (MI) and non-fatal stroke. To identify the MACE, the following potential cases identified will be adjudicated:

- All deaths
- Cardiovascular events (meeting serious criteria)
- Myocardial infarction (NARROW)
- Hospitalization for unstable angina
- Transient ischemic attack
- Stroke
- Hospitalization for cardiac failure
- Percutaneous coronary intervention

7.1.7.1.2. Thromboembolic Events

Thromboembolism events will be comprised of arterial systemic thromboembolism events (ASTE) and venous thromboembolism events (VTE) associated with deep vein thrombosis (DVT) and/or pulmonary embolism (PE). To identify the thromboembolism events, the potential cases identified using the Embolic And Thrombotic Events SMQ search will be adjudicated.

The adjudication committee will review those potential MACE and thromboembolic events and related clinical data to determine whether a MACE or thromboembolism event has developed.

The number and percentage of subjects with positively adjudicated MACE or thromboembolic events will be summarized by treatment group using PT.

By-subject listings for all randomized subjects who have potential MACE or thromboembolic events will be provided respectively.

7.1.7.2. Other Adverse Events of Special Interest

In addition to general safety parameters, MACE and Thromboembolic Events, safety information on other adverse events of special interest (AESIs) will also be analyzed. AESIs will be identified by laboratory results, SMQs, sponsor defined MSTs, or a combination of these methods as indicated below.

- All infections (defined as all PTs in the Infections and Infestations SOC)
- Serious infections (defined as all PTs in the Infections and Infestations SOC that are SAEs)
- Infections of special interest as defined below
 - a) Herpes zoster
 - b) Active tuberculosis
 - c) Opportunistic infections
- Malignancy (including lymphoma; excluding nonmelanoma skin cancer)
- Nonmelanoma skin cancer
- Gastrointestinal (GI) perforations

The number and percentage of subjects with aforementioned events of special interest will be provided by the PT for each AE of special interests.

A by-subject listing for all subjects having AE of special interests at any time will be provided for each AE of special interest.

7.2. Laboratory Evaluations

Laboratory data collected during the study will be analyzed and summarized using both quantitative and qualitative methods. Summaries of laboratory data will be provided for the Safety Analysis Set and will include data collected up to 30 days after the last dose date.

The analysis will be based on values reported in conventional units. When values are below the LOQ, they will be listed as such, and the closest imputed value will be used for the purpose of calculating summary statistics as specified in Section 3.6.

A baseline laboratory value will be defined as the last nonmissing measurement obtained on or prior to the date/time of first dose of any study drug.

For subjects who were re-randomized, the baseline laboratory value for the LTE phase will be the last available measurement obtained on or prior to the first dose date of filgotinib. The lab abnormalities after the first dose date of filgotinib will be assessed from the re-randomized baseline.

For subjects who entered LTE phase, the laboratory collected on or prior to the first dose date of any study drug for LTE will be allocated to Main Study phase. The laboratory collected after the first dose date of any study drug for LTE will be allocated to LTE phase.

A by-subject listing for laboratory test results will be provided by subject ID number and visit in chronological order for hematology, serum chemistry, and urinalysis separately. Values falling outside of the relevant reference range and/or having a severity grade of 1 or higher on the CTCAE severity grade will be flagged in the data listings, as appropriate.

No formal statistical testing is planned.

7.2.1. Summaries of Numeric Laboratory Results

Descriptive statistics of Baseline values, values at each postbaseline visit and change from Baseline at each postbaseline visit will be provided by treatment group for the following laboratory tests:

- Hematology
 - Hematocrit
 - Hemoglobin
 - Platelet count
 - Red blood cell (RBC) count
 - White blood cell (WBC) count
 - Mean corpuscular volume
 - Lymphocytes
 - Monocytes
 - Neutrophils
 - Eosinophils
 - Basophils

- Chemistry
 - Alkaline phosphatase (ALP)
 - Aspartate aminotransferase (AST)
 - Alanine aminotransferase (ALT)
 - Total bilirubin
 - Serum creatinine
 - Creatinine clearance by Cockcroft-Gault formula
 - Glucose
- Lipid
 - Triglycerides
 - Total cholesterol
 - HDL
 - LDL
 - LDL/HDL ratio

Change from baseline to a postbaseline visit will be defined as the visit value minus the baseline value. The mean, median, Q1, Q3, minimum, and maximum values will be displayed to the reported number of digits; SD values will be displayed to the reported number of digits plus 1.

Median (Q1, Q3) of the observed values for these laboratory tests will be plotted using line plot by treatment group and visit.

In the case of multiple values in an analysis window, data will be selected for analysis as described in Section 3.7.3.

7.2.2. Graded Laboratory Values

The CTCAE Version 5.0 will be used to assign toxicity grades (0 to 4) to laboratory results for analysis. Grade 0 includes all values that do not meet the criteria for an abnormality of at least Grade 1. For laboratory tests with criteria for both increased and decreased levels, analyses for each direction (i.e., increased, decreased) will be presented separately.

7.2.2.1. Treatment-Emergent Laboratory Abnormalities

Treatment-emergent laboratory abnormalities are defined as values that increase at least 1 toxicity grade from baseline at any postbaseline time point, up to and including the date of last dose of any study drug plus 30 days.

For subjects who entered LTE, treatment-emergent laboratory abnormalities during Main study phase are defined as values increase at least 1 toxicity grade from the baseline at any postbaseline time point, up to and including the first dose date of study drug for LTE.

Treatment-emergent laboratory abnormalities during LTE phase are defined as values that increase at least 1 toxicity grade from the baseline (re-randomized baseline for re-randomized subjects) at any postbaseline time point after first dose date of study drug for LTE, up to and including the date of last dose of any study drug plus 30 days.

If the relevant baseline laboratory value is missing, any abnormality of at least Grade 1 observed within the time frame specified above will be considered treatment emergent.

7.2.2.2. Treatment-Emergent Marked Laboratory Abnormalities

Treatment-emergent marked laboratory abnormalities are defined as values that increase at least 3 toxicity grade from baseline at any postbaseline time point, up to and including the date of last dose of any study drug plus 30 days.

For subjects who entered LTE, treatment-emergent marked laboratory abnormalities during Main study phase are defined as values increase at least 3 toxicity grade from the baseline at any postbaseline time point, up to and including the first dose date of study drug for LTE.

Treatment-emergent marked laboratory abnormalities during LTE phase are defined as values that increase at least 3 toxicity grade from the baseline (re-randomized baseline for re-randomized subjects) at any postbaseline time point after first dose date of study drug for LTE, up to and including the date of last dose of any study drug plus 30 days.

If the relevant baseline laboratory value is missing, any Grade 3 or higher values observed within the timeframe specified above will be considered treatment emergent marked abnormalities.

7.2.2.3. Summaries of Laboratory Abnormalities

Laboratory data that are categorical will be summarized using the number and percentage of subjects in the study with the given response at baseline and each scheduled postbaseline visit.

The following summaries (number and percentage of subjects) for treatment-emergent laboratory abnormalities will be provided by lab test and treatment group; subjects will be categorized according to the most severe postbaseline abnormality grade for a given laboratory test:

- Graded laboratory abnormalities
- Grade 3 or higher laboratory abnormalities
- Marked laboratory abnormalities

For all summaries of laboratory abnormalities, the denominator is the number of subjects with nonmissing postbaseline values up to 30 days after last dosing date.

By-subject listings of treatment-emergent Grade 3 or higher laboratory abnormalities and marked laboratory abnormalities will be provided separately by subject ID number and visit in chronological order. These listings will include all test results that were collected throughout the study for the lab test of interest, with all applicable severity grades or abnormal flags displayed.

7.2.3. Liver-related Laboratory Evaluations

Liver-related abnormalities after initial study drug dosing will be examined and summarized using the number and percentage of subjects who were reported to have the following laboratory test values for postbaseline measurements:

- Aspartate aminotransferase (AST): (a) > 3 times of the upper limit of reference range (ULN); (b) > 5 x ULN; (c) > 10 x ULN
- Alanine aminotransferase (ALT): (a) > 3 x ULN; (b) > 5 x ULN; (c) > 10 x ULN
- AST or ALT: (a) > 3 x ULN; (b) > 5 x ULN; (c) > 10 x ULN
- Total bilirubin: > 2 x ULN
- Alkaline phosphatase (ALP) > 1.5 x ULN
- AST or ALT > 3 x ULN and total bilirubin: (a) > 1.5 x ULN; (b) > 2 x ULN

The summary will include data from all postbaseline visits up to 30 days after the last dose of study drug. For individual laboratory tests, subjects will be counted once based on the most severe postbaseline values. For both the composite endpoint of AST or ALT and total bilirubin, subjects will be counted once when the criteria are met at the same postbaseline visit date. The denominator is the number of subjects in the Safety Analysis Set who have nonmissing postbaseline values of all relevant tests at the same postbaseline visit date. A listing of subjects who met at least 1 of the above criteria will be provided.

7.2.4. Complete Blood Count-Related Laboratory Evaluations

Complete blood count (CBC)-related abnormalities such as anemia, leucopenia, neutropenia, lymphopenia, and thrombocytopenia after initial study drug dosing will be examined and summarized using the number and percentage of subjects who were reported to have the following laboratory test values for postbaseline measurements:

- Hemoglobin: (a) any postbaseline worsening CTCAE grade from baseline; (b) baseline value of less than Grade 3 and increase to Grade 3 or higher at worst postbaseline; (c) baseline value of less than Grade 3 and increase to Grade 4 at worst postbaseline
- WBC count: (a) any postbaseline worsening CTCAE grade from baseline; (b) baseline value of less than Grade 3 and increase to Grade 3 or higher at worst postbaseline; (c) baseline value of less than Grade 3 and increase to Grade 4 at worst

- Absolute neutrophil count: (a) any postbaseline worsening CTCAE grade from baseline; (b) baseline value of less than Grade 3 and increase to Grade 3 or higher at worst postbaseline; (c) baseline value of less than Grade 3 and increase to Grade 4 at worst postbaseline
- Lymphocyte count: (a) any postbaseline worsening CTCAE grade from baseline; (b) baseline value of less than Grade 3 and increase to Grade 3 or higher at worst postbaseline; (c) baseline value of less than Grade 3 and increase to Grade 4 at worst postbaseline
- Platelet count: (a) any postbaseline worsening CTCAE grade from baseline; (b) baseline value of less than Grade 3 and increase to Grade 3 or higher at worst postbaseline; (c) baseline value of less than Grade 3 and increase to Grade 4 at worst postbaseline

The summary will include data from all postbaseline visits up to 30 days after the last dose of any study drug.

7.3. Body Weight and Vital Signs

Descriptive statistics will be provided by treatment group for body weight, BMI and vital signs (systolic and diastolic pressures (mmHg), pulse (beats/min)) as follows:

- Baseline value
- Values at each postbaseline visit
- Change from baseline at each postbaseline visit

A baseline value will be defined as the last available value collected on or prior to the date/time of first dose of study drug.

For subjects who were re-randomized, the baseline value for LTE phase will be defined as the last available value collected on or prior to the date/time of the first dose of study drug for LTE.

For subjects who entered LTE phase, the body weight, BMI and vital signs collected on or prior to the first dose date of any study drug for LTE will be allocated to Main Study phase. The body weight, BMI and vital signs collected after the first dose date of any study drug for LTE will be allocated to LTE phase.

Change from baseline to a postbaseline visit will be defined as the postbaseline value minus the baseline value. Body weight and vital signs measured at unscheduled visits will be included for the baseline value selection.

In the case of multiple values in an analysis window, data will be selected for analysis as described in Section 3.7.3. No formal statistical testing is planned.

A by-subject listing of vital signs will be provided by subject ID number and visit in chronological order. In the same manner, a by-subject listing of body weight, height, and BMI will be provided separately.

7.4. Prior and Concomitant Medications

Medications collected at screening and during the study will be coded using the current version of the World Health Organization (WHO) Drug dictionary.

All the analyses in this section will be performed for general prior/concomitant medications and PsA-specific prior/concomitant medications separately, unless otherwise specified.

7.4.1. Prior Medications

Prior medications are defined as any medications taken before a subject took the first study drug.

Prior medications will be summarized by preferred name using the number and percentage of subjects for each treatment group and overall. A subject reporting the same medication more than once will be counted only once when calculating the number and percentage of subjects who received that medication. The summary will be provided by preferred term in order of descending overall frequency. For drugs with the same frequency, sorting will be done alphabetically.

For the purposes of analysis, any medication with a start date prior to the first dosing date of study drug will be included in the prior medication summary regardless of when the stop date is. If a partial start date is entered the medication will be considered prior unless the month and year (if day is missing) or year (if day and month are missing) of the start date are after the first dosing date. Medications with a completely missing start date will be included in the prior medication summary, unless otherwise specified.

Summaries will be based on the Safety Analysis Set. No formal statistical testing is planned.

7.4.2. Concomitant Medications

Concomitant medications are defined as medications taken while a subject took study drug. Use of concomitant medications will be summarized by preferred name using the number and percentage of subjects for each treatment group and overall. A subject reporting the same medication more than once will be counted only once when calculating the number and percentage of subjects who received that medication. The summary will be ordered by preferred term in descending overall frequency. For drugs with the same frequency, sorting will be done alphabetically.

For the purposes of analysis, any medications with a start date prior to or on the first dosing date of study drug and continued to be taken after the first dosing date, or started after the first dosing date but prior to or on the last dosing date of study drug will be considered concomitant medications. Medications started and stopped on the same day as the first dosing date or the last dosing date of study drug will also be considered concomitant. Medications that stopped on the same day as the first dosing date will be considered concomitant. Medications with a stop date prior to the date of first dosing date of study drug or a start date after the last dosing date of study drug will be excluded from the concomitant medication summary. If a partial stop date is

entered, any medication with the month and year (if day is missing) or year (if day and month are missing) prior to the date of first study drug administration will be excluded from the concomitant medication summary. If a partial start date is entered, any medication with the month and year (if day is missing) or year (if day and month are missing) after the study drug stop date will be excluded from the concomitant medication summary. Medications with completely missing start and stop dates will be included in the concomitant medication summary, unless otherwise specified. Summaries will be based on the Safety Analysis Set. No formal statistical testing is planned.

For subjects who entered LTE, concomitant medications with a start date prior to the first dose date of any study drug for LTE will be allocated to the Main Study phase. Concomitant medications with a start date on or after first dose date of any study drug for LTE will be allocated to the LTE phase.

For subjects who entered LTE, a concomitant medication with incomplete start date that is prior to the month and year (or year) of the first dose date of any study drug for LTE will be allocated to the Main Study phase. A concomitant medication with incomplete start date that is after the month and year (or year) of the first dose date of any study drug for LTE will be allocated to the LTE phase.

In addition, a concomitant medication with completely missing start date or incomplete start date that is same as the month and year (or year) of the first dose date of study drug for LTE, and stop date that is prior to the date (or month and year if day is not recorded; or year alone if month is not recorded) of the first dose of study drug for LTE will be allocated to the Main Study phase. A concomitant medication with completely missing start date or incomplete start date that is same as the month and year (or year) of the first dose date of study drug for LTE, and stop date that is missing, or the same as, or after the date (or month and year if day is not recorded; or year alone if month is not recorded) of the first dose of study drug for LTE will be allocated to the LTE phase.

Summaries will be based on the Safety Analysis Set. No formal statistical testing is planned.

All prior and concomitant medications (other than per-protocol study drugs) will be provided in a by-subject listing sorted by subject ID number and administration date in chronological order.

7.5. Other Safety Measures

A data listing will be provided for subjects who become pregnant during the study.

7.6. Changes From Protocol-Specified Safety and Other Analyses

Safety analyses based on treatment policy estimand will not be performed.

CCI

9. SOFTWARE

SAS® Software Version 9.4. SAS Institute Inc., Cary, NC, USA.

nQuery Advisor(R) Version 4.0. Statistical Solutions, Cork, Ireland.

10. SAP REVISION

Revision Date (DD MMM YYYY)	Section	Summary of Revision	Reason for Revision

Appendix 1. Heath Assessment Questionnaire Disability Index (HAQ-DI)

The HAQ-DI score is defined as the average of the scores of eight functional categories (dressing and grooming, arising, eating, walking, hygiene, reach, grip, and other activities), usually administered by the subject. Responses in each functional category are collected as 0 (without any difficulty) to 3 (unable to do a task in that area), with or without aids or devices.

The highest score for questions in each category (range 0 to 3) determines the score for the category, unless aids or devices are required. Dependence on equipment or physical assistance increases a lower score (ie, scores of 0 or 1) to the level of 2 to more accurately represent underlying disability. The eight category scores are averaged into an overall HAQ-DI score on a scale from 0 (no disability) to 3 (completely disabled) when 6 or more categories are nonmissing. If more than 2 categories are missing, the HAQ-DI score is set to missing. The HAQ-DI can be treated as a continuous measure.

The HAQ-DI score using aids (and/or devices) is computed by taking the maximum score of the questions in each category (range: [0, 3]) and whether or not aids/devices are used (0 or 1):

$$A = \begin{aligned} & \max(\text{dressing \& grooming category questions, } 2 * \text{aids indicator}) + \\ & \max(\text{rising category questions, } 2 * \text{aids indicator}) + \\ & \max(\text{eating category questions, } 2 * \text{aids indicator}) + \\ & \max(\text{walking category questions, } 2 * \text{aids indicator}) + \\ & \max(\text{hygiene category questions, } 2 * \text{aids indicator}) + \\ & \max(\text{reach category questions, } 2 * \text{aids indicator}) + \\ & \max(\text{grip category questions, } 2 * \text{aids indicator}) + \\ & \max(\text{usual activities category questions, } 2 * \text{aids indicator}) \end{aligned}$$

$$\text{HAQ-DI} = A / (\text{total number of categories with at least 6 nonmissing})$$

The following table shows the contribution of the 43 questions used to calculate the HAQ-DI:

HAQ-DI Category:	Category questions: At least 6 categories must have scores to compute the HAQ-DI.		HAQ-DI Category Score with Aids/Devices Calculation:
	Category Questions	Aids/Devices Indicators	
Dressing / Grooming	HAQ0101, HAQ0102 (DRESS, HAIR)	HAQ0114, HAQ0119 (DRSG, GROOM)	
Using each question with a scale of 0-3, calculate the category score as the maximum of the category questions.
 
If the Aids/Devices indicator is “No”, no need to adjust the category score.
 
If the Aids/Devices indicator is “Yes” and the category score is <2, then the category score with the Aids/Devices is set to 2.
 
If the Aids/Devices indicator is “Yes” and the category score is ≥2, then the category score with Aids/Devices is the calculated category score without adjustment.
 
For example: The Dressing/Grooming category score is 2 if subject answered 1 for both questions 1 and 2 and “Yes” for both question 14 and 19.
 
In the HAQ-DI score calculation, questions on other device/aids will not be used.

Arising	HAQ0103, HAQ0104 (STAND, BED)	HAQ0116, HAQ0120 (CHAIR, ARISING)	
Eating	HAQ0105, HAQ0106, HAQ0107 (MEAT, LIFT, MILK)	HAQ0115, HAQ0121 (UTENSIL, EAT)	
Walking	HAQ0108, HAQ0109 (WALK, STEPS)	HAQ0110, HAQ0111, HAQ0112, HAQ0113, HAQ0122 (CANE, WALKER, CRUTCH, WHEEL, WALKING)	
Hygiene	HAQ0123, HAQ0124, HAQ0125 (WASH, BATH, TOILET)	HAQ0134, HAQ0135, HAQ0137, HAQ0139, HAQ0142 (RAISEAT, BATHBAR, BATHSEAT, LONGBATH, HYGIENE)	
Reach	HAQ0126, HAQ0127 (REACH, BEND)	HAQ0138, HAQ0143 (LONGRCH, REACH)	
Grip	HAQ0128, HAQ0129, HAQ0130 (OPENCAR, JAR, FAUCET)	HAQ0136, HAQ0144 (JAROPEN, GRIP)	
Activity	HAQ0131, HAQ0132, HAQ0133 (SHOP, INCAR, CHORES)	HAQ0145 (ERRAND)	

Handling Missing Data: If no more than 2 categories have missing category scores, then the HAQ-DI is the mean of the nonmissing category scores. Otherwise, the HAQ-DI score is set to missing.

If any of the category questions are missing, but the aids/device indicator is nonmissing, the category score can still be computed. However, if all category questions and its aids/device indicators are missing, then the category score is considered missing.

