Appendix 9. HAQ-DI: Health Assessment Questionnaire – Disability Index

HEALTH ASSESSMENT QUESTIONNAIRE

Name _____ Date _____

PATKEY# _____
 QUESTDAT _____
 -
 HAQADMIN _____
 QUESTYPE _____
 PMSVIS _____
 RASTUDY _____
 QUESTNUM _____
 DRESSNEW _____
 RISENEW _____
 EATNEW _____
 WALKNEW _____
 DRSGASST _____
 RISEASST _____
 EATASST _____
 WALKASST _____
 -

In this section we are interested in learning how your illness affects your ability to function in daily life. Please feel free to add any comments on the back of this page.

Please check the response which best describes your usual abilities OVER THE PAST WEEK:

	Without ANY Difficulty	With SOME Difficulty	With MUCH Difficulty	UNABLE To Do	
DRESSING & GROOMING					
Are you able to:					
- Dress yourself, including tying shoelaces and doing buttons?	___	___	___	___	
- Shampoo your hair?	___	___	___	___	
ARISING					
Are you able to:					
- Stand up from a straight chair?	___	___	___	___	
- Get in and out of bed?	___	___	___	___	
EATING					
Are you able to:					
- Cut your meat?	___	___	___	___	
- Lift a full cup or glass to your mouth?	___	___	___	___	
- Open a new milk carton?	___	___	___	___	
WALKING					
Are you able to:					
- Walk outdoors on flat ground?	___	___	___	___	
- Climb up five steps?	___	___	___	___	
Please check any AIDS OR DEVICES that you usually use for any of these activities:					
___ Cane	___ Devices used for dressing (button hook, zipper pull, long-handled shoe horn, etc.)				
___ Walker	___ Built up or special utensils				
___ Crutches	___ Special or built up chair				
___ Wheelchair	___ Other (Specify: _____)				
Please check any categories for which you usually need HELP FROM ANOTHER PERSON:					
___ Dressing and Grooming	___ Eating				
___ Arising	___ Walking				

Please check the response which best describes your usual abilities OVER THE PAST WEEK:

	Without ANY Difficulty	With SOME Difficulty	With MUCH Difficulty	UNABLE To Do		
HYGIENE						
Are you able to:						
- Wash and dry your body?	_____	_____	_____	_____		
- Take a tub bath?	_____	_____	_____	_____		
- Get on and off the toilet?	_____	_____	_____	_____	HYGNNEW_____	
REACH						
Are you able to:						
- Reach and get down a 5 pound object (such as a bag of sugar) from just above your head?	_____	_____	_____	_____		
- Bend down to pick up clothing from the floor?	_____	_____	_____	_____	REACHNEW_____	
GRIP						
Are you able to:						
- Open car doors?	_____	_____	_____	_____		

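### SAP Appendix 1 lets a HAQ-DI category with no answered question score 0 (no difficulty) when aids are recorded as No

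*SAP*

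**What the plan says.** SAP Appendix 1 describes category scoring in three places.

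- **Formula.** Each of the eight categories is max(category questions, 2 × aids indicator). Questions run from 0 (no difficulty) to 3, and the indicator is 0 or 1.
- **Stepwise table.** The category score is the maximum of its questions. For an indicator of No, the table adds: "If the Aids/Devices indicator is “No”, no need to adjust the category score".
- **Handling Missing Data.** "If any of the category questions are missing, but the aids/device indicator is nonmissing, the category score can still be computed". The only route to a missing category is the next sentence: "However, if all category questions and its aids/device indicators are missing, then the category score is considered missing". HAQ-DI is the mean of the nonmissing categories, and is missing if more than two categories are missing.

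The sample form in Protocol Appendix 9 collects aids as tick boxes: "Please check any AIDS OR DEVICES that you usually use for any of these activities". Help from another person is collected the same way. Neither list has a No option.

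HAQ-DI is used in three places: change at Week 12 is a key secondary endpoint (SAP 6.3), it is one of the five ACR20 and ACR50 items of which three must improve (SAP 6.2.1.1, 6.3.1.1), and a score of 0.5 or below is one of the seven MDA criteria of which five must be met (SAP 6.3.1.5).

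**The concern.** When every question in a category is unanswered and the aids indicator is No, the missing-data paragraph does not make the category missing. The formula then has one usable argument, 2 × 0, and can return only 0. Nonresponse receives the best possible score.

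That zero counts as a nonmissing category, so it also gets past the safeguard that withholds HAQ-DI when too little was answered. The effect enters before any of the SAP's planned missing-data handling. A score that should have been prorated from the other categories, or left missing and passed to the mixed model, multiple imputation or observed-case analysis, arrives as an observed value that is too low.

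The stepwise table gives no maximum for the same case. Two programmers working from different parts of Appendix 1 could produce different HAQ-DI values from the same data.

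**Working it through.** **Inputs.** The category formula, the missing-data paragraph, the stepwise table and the minimum of 6 of 8 categories come from SAP Appendix 1. The response thresholds are an improvement of at least 20% (ACR20 item) or 50% (ACR50 item), and HAQ-DI of 0.5 or below (MDA criterion). Percent improvement is 100 × (baseline − later value) / baseline (SAP 6.2.1.1). One assumption is needed: the maximum ignores missing arguments. SAP Section 9 names SAS 9.4, but the plan does not say how a maximum over missing values is taken.

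**Reproducing the SAP's own example.** Both Dressing/Grooming questions at 1 with aids Yes: max(1, 1, 2 × 1) = 2, as the SAP states. Formula and table agree here.

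**All questions in a category blank:**

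| Aids indicator | Formula with missing-data paragraph | Stepwise table |
|---|---|---|
| Yes | 2 | 2 |
| No | 2 × 0 = 0 | no score |
| Missing | missing | no score |

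The disagreement is confined to the No row.

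**Unchanged subject, all eight categories at 1 (baseline 8/8 = 1.00), later blanks with aids No:**

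| Blank categories | As written | Apparent improvement | Blanks set to missing |
|---|---|---|---|
| 1 | 7/8 = 0.875 | 12.5% | 7/7 = 1.00 |
| 2 | 6/8 = 0.75 | 25% (meets ACR20 item) | 6/6 = 1.00 |
| 3 | 5/8 = 0.625 | 37.5% | missing (5 categories) |
| 4 | 4/8 = 0.50 | 50% (meets ACR50 item and MDA criterion) | missing (4 categories) |

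For any equal nonzero category score, the apparent reduction is k/8 with k blanks.

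**One blank can be enough.**

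- Categories 2, 2, 1, 1, 1, 1, 0, 0 average 8/8 = 1.00. With one of the 2s blank, the score as written is 6/8 = 0.75 (25%). With that category set to missing it is 6/7 = 0.857 (14.3%).
- Five categories at 1 and three at 0 give 5/8 = 0.625, which does not meet the MDA criterion. With one of the 1s blank, the score as written is 4/8 = 0.50, which meets it. With that category set to missing it is 4/7 = 0.571, which does not.

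**Blank only at baseline.** All categories are truly 1 throughout. One baseline blank gives 0.875 and two give 0.75. A complete later score of 1.00 then shows (0.875 − 1) / 0.875 = −14.3% or (0.75 − 1) / 0.75 = −33.3%, an apparent worsening. MDA uses the absolute score at the visit, so for that criterion a blank can only help.

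**The case against.** The strongest reply is that Appendix 1 never prints a 0 for an unanswered category. The sentence about missing questions can be read as covering a partly answered category, where a maximum of the remaining answers is reasonable, and the stepwise table gives no score when nothing was answered. That reading is available, but it does not settle the matter. The following sentence requires the indicators to be missing too before the category is missing. At best the case is undefined and the parts of the appendix conflict.

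Three stronger inferences are tempting, and the documents do not support them.

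- **That the error always favours improvement.** A blank only at baseline pushes HAQ-DI change and the ACR item the other way, as shown above. Only the MDA criterion is one-directional.
- **That the more-than-two-missing rule can never apply, or that an empty form would score 0.** This needs unticked boxes to be stored as No, which neither document states. The SAP treats a missing indicator as a separate state, and Protocol 6.6.3.1 calls the appendix forms examples and refers to the electronic assessment materials for instructions. If unticked boxes are stored as No, the rule would rarely apply. If an untouched form is stored as missing, it works as intended.
- **That the comparison between arms is biased.** Nothing in the documents suggests that blanks would differ between double-blind arms.

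It also stands that HAQ-DI cannot create a responder by itself. ACR needs both joint counts and three of five items, and MDA needs five of seven criteria. A category truly at 0 loses nothing by being blank.

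**Conclusion.** The point holds as a scoring defect. Followed literally, and with a maximum that ignores missing values, Appendix 1 gives a fully unanswered category with aids No the best score and counts it as answered, while the stepwise table gives no score. With equal nonzero category scores, each such category lowers HAQ-DI by 12.5%. Two post-baseline blanks can meet the ACR20 item without real change, and a single blank can do so, or meet the MDA criterion, in less even profiles.

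The practical effect cannot be estimated, because the documents give neither the frequency of blank categories nor whether the electronic questionnaire allows skipped items. It may be nil. The trial stopped after 67 enrolled subjects and its p-values are nominal (SAP 1.3, 3.4), which limits the inferential stakes. Small arms do give each subject more weight: if the 2:2:1:2 ratio held, a filgotinib or placebo arm has about 67 × 2/7 ≈ 19 subjects, so one tipped responder moves a rate by about 1/19 ≈ 5 percentage points. SAP 6.5 plans no sensitivity analyses that might show it.

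**What to change.** Replace the missing-data sentences in SAP Appendix 1 with one rule, and bring the stepwise table into line: when no question in a category is answered and no aid or help is ticked for it, the category score is missing; then apply the existing requirement of at least six nonmissing categories. State how unticked boxes are stored.

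The cost is one sentence and a line of code. If no category was left wholly blank, no result changes. There are small downsides:

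- A few more HAQ-DI scores may be missing. Post-baseline gaps in HAQ-DI change fall to the mixed model, an undeterminable Week 12 ACR20 to multiple imputation, and other binary endpoints to the observed-case rules. A missing baseline HAQ-DI would drop the subject from the HAQ-DI mixed model, which requires a baseline value (SAP 6.3.2).
- A blank category with an aid ticked keeps its score of 2 while one without is dropped, which tilts the average slightly upward.
- Averaging the answered categories is not exact. In the profile 2, 2, 1, 1, 1, 1, 0, 0, leaving both 2s blank still gives 4/6 = 0.667, an apparent 33.3% improvement, against 4/8 = 0.50 (50%) as written.
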